7. PLANNED ANALYSIS

For End-Of-Text tables, the set of summary statistics is: N / Mean / SD / Min / Q1 / Median / Q3 / Max. In descriptive statistics tables, mean, sd and median will be rounded to one additional digit than the raw data

Tabulations of frequencies for categorical data will include all categories depicted in the eCRF and will display the number of observations in a category as well as the percentage (%) relative to the respective treatment group (unless otherwise specified, all subjects in the respective subject set whether they have non-missing values or not). Percentages will be rounded to one decimal place. The category missing will be displayed only if there are actually missing values.

In Phase II, all analyses will be based on the treatment group as treated. If not specified otherwise, all analyses will be based on all randomised patients that have been treated.

Only descriptive analyses or listings will be provided due to the low patient numbers.

7.1 DEMOGRAPHIC AND OTHER BASELINE CHARACTERISTICS

Only descriptive statistics are planned for this section of the report.

7.2 CONCOMITANT DISEASES AND MEDICATION

Concomitant diseases and medication will be listed. No summary tables are planned.

7.2.1 Baseline conditions and targeted risk factors

The baseline conditions will be included as coded items using the current Medical Dictionary for Regulatory Activities (MedDRA) version in use at BI at the time of database lock. They will be listed by MedDRA system organ class (SOC) and Preferred Term. No summary tables are planned.

Targeted risk factors for progression to severe COVID-19 infection as collected on the corresponding eCRF page will be listed.

7.2.2 Concomitant therapies

The following categories of concomitant therapies have been created:

- Previous therapies
 - Defined as treatments with an end date before trial drug intake.
- Baseline therapies
 - Defined as treatments with a start date before trial drug intake and taken after or on the day of the trial drug intake.

- On-treatment concomitant therapies
 - Defined as treatments with a start date after or on the day of trial drug intake and before or on the last day of the residual effect period (for details, please see Section 6.1).
- Post-study therapies
 - Defined as treatments with a start date after the end of the residual effect period (for details, please see Section 6.1).

Concomitant therapies will be listed. No summary tables are planned.

7.3 TREATMENT COMPLIANCE

This section is not applicable as no analyses on treatment compliance are planned.

7.4 PRIMARY ENDPOINT

The primary endpoint in Phase II is the time-weighted change from baseline in viral shedding over 8 days in site collected NP swabs by RT-qPCR. Please refer to Section 7.1, 7.2.2 and 7.2.3 of the CTP for additional information on the underlying hypotheses and assessment strategy.

7.4.1 Primary analysis of the primary endpoint

Only descriptive analyses will be performed.

Evaluation will be performed on the mITT set and will take into account all data up to and including Day 8.

Missing values will not be imputed and since a linear trajectory on the log scale is expected.

7.5 SECONDARY ENDPOINT(S)

7.5.1 Key secondary endpoint(s)

This section is not applicable as no key secondary endpoint has been specified in the protocol.

7.5.2 (Other) Secondary endpoints

7.5.2.1 Time-weighted change from baseline in viral shedding over 29 days in site collected NP swabs by RT-qPCR

Only descriptive analyses will be performed.

Evaluation will be performed on all patients included in the randomised set that received any amount of study drug and who have at least a measurable baseline value (above LLOQ) of SARS-CoV-2 RNA by site collected NP swab and a second measurement after baseline.

All SARS-CoV-2 RNA measurements by site collected NP swab up to and including Day 29 will be used in the analysis.

Viral load will be plotted individually for each patient over time.

7.5.2.2 Loss of detection of SARS-CoV-2 RNA by site collected NP swab at Day 4, 8, 15, 22 and 29

The number and proportion of patients with loss of detection of SARS-CoV-2 RNA by site collected NP swab will be calculated on Day 4, 8, 15, 22 and 29. Please refer to Section 6.7 for the definition of time-windowing rules.

Evaluation will be performed on all patients included in the randomised set that received any amount of study drug and, who have at least a measurable baseline value (above LLOQ) of SARS-CoV-2 RNA by site collected NP swab and a second measurement after baseline.

7.7 EXTENT OF EXPOSURE

Exposure data will be listed for all patients treated.

7.8 SAFETY ANALYSIS

All safety analyses will be performed on the treated set.

7.8.1 Adverse Events

Unless otherwise specified, the analyses of AEs will be descriptive in nature. All analyses of AEs will be based on the number of subjects with AEs and NOT on the number of AEs.

The analysis of AEs will be based on the concept of treatment emergent AEs. That means that all adverse events occurring after drug intake until the end of the residual effect period (+90 days thereafter) will be assigned to the treatment. All adverse events occurring before drug intake will be assigned either to 'screening' or 'post-randomisation' (for listings only). All adverse events occurring after drug intake +90 days will be assigned to 'post-study' (for listings only). For details on the treatment definition, see Section 6.1.

All AEs that occur at any time during trial participation after drug administration, including all AEs occurring between drug intake (included) and up to the end of the residual effect period analyses will be included in the analysis.

An overall summary of adverse events will be presented.

The frequency of subjects with any adverse events will be summarised by treatment group, primary system organ class and preferred term. The system organ classes will be sorted according to the standard sort order specified by EMA, preferred terms will be sorted by decreasing frequency in the BI 767551 arm (within SOC).

In addition, infusion related reactions and inhalation related reactions will be listed based on the data reported on the dedicated eCRF pages.

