Possible or known risks of clinical relevance for this trial	Summary of data, rationale for the risk	Mitigation strategy
Viral Resistance	There is a potential risk of treatment failure due to the development of viral variants that are resistant to BI 767551 (viral resistance). It is possible that resistance-associated variants to BI 767551 could have cross- resistance to other monoclonal antibodies targeting the receptor binding domain of SARS-CoV-2. The clinical impact is not known. Resistant strains of virus can also arise independent of antibody use.	Viral RNA genome samples will be collected for each patient in this trial. Trial patients will be carefully monitored as part of the reviews by the DMC who will have access to unblinded data. Any lack of responsiveness may finally be assessed based on the genomic analysis of samples and the circulating variants at that time.
Antibody- dependent enhancement	Fc receptor-mediated effects may enhance disease or infection by increased viral replication or immunological reaction (e.g., in pulmonary tissues). ADE effect has not been reported in Phase II clinical trial of a SARS-CoV-2-neutralizing monoclonal antibody (LY- CoV555,)) administered to recently infected outpatients (R20-4045).	Patients will be carefully monitored for potential worsening of symptoms, including respiratory distress.

33563257-02Clinical Trial ProtocolPage 34 of 12Proprietary confidential information © 2021 Boehringer Ingelheim International GmbH or one or more of its affiliated companies

Table 1.4.2:1 Overview of trial related risks (continued)

Possible or known risks of clinical relevance for this trial	Summary of data, rationale for the risk	Mitigation strategy	
Blunting of vaccine response	Administration of BI 767551 may result in blunting of SARS- CoV-2 vaccine responses should these vaccines become available.	Monitoring of the immune response to vaccination or delayed or repeated vaccination may be required. Patients with previous SARS-CoV-2 vaccination are excluded.	
Drug-induced liver injury (DILI)	Rare but severe event, that must be monitored in all clinical studies, independent of intervention and indication, thus under constant surveillance by sponsors and regulators.	Timely detection, evaluation, and follow-up of laboratory alterations in selected liver laboratory parameters to ensure patients' safety.	
Trial procedures			

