7.2.6 Safety analyses

Adverse events will be coded using the Medical Dictionary for Drug Regulatory Activities (MedDRA). Standard BI summary tables and listings will be produced. All adverse events with an onset between start of treatment and end of the REP, a period of 90 days after the last dose of trial medication, will be assigned to the on-treatment period for evaluation.

All treated patients will be included in the safety analysis. In general, safety analyses will be descriptive in nature and will be based on BI standards. No hypothesis testing is planned.

Statistical analysis and reporting of adverse events will concentrate on treatment-emergent adverse events, i.e. all adverse events occurring between start of treatment and end of the REP. Adverse events that start before first drug intake and deteriorate under treatment will also be considered as 'treatment-emergent'.

Frequency, severity (as graded according to DAIDS Table 5.2.6.1.5:1 [R21-0379]), and causal relationship of adverse events will be tabulated by system organ class and preferred term after coding according to the current version of the Medical Dictionary for Drug Regulatory Activities (MedDRA) at database lock.

Laboratory data will be analysed both quantitatively as well as qualitatively. The latter will be done via comparison of laboratory data to their reference ranges. Values outside the reference range as well as values defined as clinically relevant will be summarised. Treatment groups will be compared descriptively with regard to distribution parameters as well as with regard to frequency and percentage of patients with abnormal values or clinically relevant abnormal values.

Vital signs, physical examinations, or other safety-relevant data observed at screening, baseline, during the course of the trial and at the end-of-trial evaluation will be assessed with regard to possible changes compared to findings before start of treatment.

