3. INTRODUCTION

As per ICH E9 (1), the purpose of this document is to provide a more technical and detailed elaboration of the principal features of the analysis described in the protocol, and to include detailed procedures for executing the statistical analysis of the primary and secondary variables and other data.

This TSAP assumes familiarity with the Clinical Trial Protocol (CTP), including Protocol Amendments. In particular, the TSAP is based on the planned analysis specification as written in CTP Section 7 "Statistical Methods and Determination of Sample Size". Therefore, TSAP readers may consult the CTP for more background information on the study, e.g., on study objectives, study design and population, treatments, definition of measurements and variables, planning of sample size, randomization.

This TSAP covers only Phase II of the study. As the study has been terminated early by BI, only a restricted set of analyses are planned.

SAS[®] Version 9.4 will be used for all analyses.

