4. CHANGES IN THE PLANNED ANALYSIS OF THE STUDY

Following BI's decision to terminate the development program for BI 767551 (anti-SARS-CoV-2 neutralizing antibody (nAb) under investigation for SARS-CoV-2-infected patients), study 1487-0001 has been discontinued as of 25 June 2021, with only a few patients screened (7), and randomized (5). Considering this low number of patients randomized in the study, the following changes to the planned analysis will be implemented:

- No model based statistical analysis will be performed. Descriptive statistics will be provided for primary and secondary endpoints. Further endpoints will not be analysed but data will be listed.
- No subgroup analyses will be performed.
- Unless described otherwise in Section 6.6, missing data will not be imputed.
- PK and ADA samples will not be analysed.

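### SAP 7.8.1 sends every adverse event that begins before dosing to listings only, without the protocol's rule that such an event becomes treatment-emergent if it worsens under treatment

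*SAP*

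**What the plan says.** Protocol 7.2.6 centres the safety reporting on one class of event: "Statistical analysis and reporting of adverse events will concentrate on treatment-emergent adverse events". Two routes lead into that class. The first is occurrence between start of treatment and the end of the residual effect period, 90 days after the dose. The second is worsening: "Adverse events that start before first drug intake and deteriorate under treatment will also be considered as 'treatment-emergent".

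SAP 7.8.1 also says that its analysis rests on the treatment-emergent concept, but it sets out only the first route: "all adverse events occurring after drug intake until the end of the residual effect period (+90 days thereafter) will be assigned to the treatment". For events before the dose it says: "All adverse events occurring before drug intake will be assigned either to 'screening' or 'post-randomisation' (for listings only". The later sentence on scope is likewise confined to the time after dosing: "All AEs that occur at any time during trial participation after drug administration". For detail the section refers to SAP 6.1, which cuts the study periods at drug intake and has no rule on worsening.

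SAP Section 3 says that "the TSAP is based on the planned analysis specification as written in" protocol Section 7. SAP Section 4 introduces its list of departures with "the following changes to the planned analysis will be implemented". The list covers model-based analysis, further endpoints, subgroups, imputation, and PK and ADA samples. The definition of treatment-emergent is not on it.

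**The concern.** The two documents classify the same event differently, and the SAP does not declare the difference. Protocol 5.2.6.2.1 collects AEs from consent. Protocol 6.2.2 allows up to 3 days from consent to randomisation, and protocol 3.1 puts the dose on the day of randomisation. All patients have symptoms at entry. So a complaint can begin after consent, be logged as an AE, and then get worse after the infusion or inhalation.

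Worsening has safety meaning here. For antibody-dependent enhancement, the risk table in protocol 1.4.2 says: "Patients will be carefully monitored for potential worsening of symptoms, including respiratory distress". That sentence is about monitoring patients, not about tabulating events, but it shows why the protocol's worsening clause is not a formality. Dropping the clause can only lower the AE counts in the summary tables; it cannot raise them.

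**Working it through.** No figure in the plan needs reproducing, because the point is a classification rule. I set the two rules against each possible pattern of event.

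| Pattern | Protocol 7.2.6 | SAP 7.8.1 |
|---|---|---|
| 1. Onset after dosing, within the residual effect period | Treatment-emergent | Tabulated |
| 2. Onset between consent and dosing, no worsening | Not treatment-emergent | Listed only |
| 3. Onset between consent and dosing, worsens after dosing, kept as one record | Treatment-emergent | Listed only |
| 4. As 3, but the worsening is entered as a new record with post-dose onset | Treatment-emergent | Tabulated |
| 5. Present before consent, worsens after dosing, worsening recorded as an AE with post-dose onset | Treatment-emergent | Tabulated |

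The rules part only in row 3. Three points support the table.

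- **Row 5.** Protocol 6.2.1 records signs and symptoms present before consent as medical history. Protocol 5.2.6.1.1 requires worsening of the underlying disease or of a pre-existing condition to be recorded as an AE. Given a post-dose onset, that AE falls in the treatment or residual effect period and is tabulated.
- **Rows 3 and 4.** The documents do not say whether a worsened AE is split into a new record. Protocol 5.2.6.1.5 has intensity recorded in the CRF, and protocol 8.3.1 has onset and end dates. Neither describes how a change of intensity within one event is captured.
- **Wording.** The SAP speaks of events occurring, not starting, before intake. I read this as onset, because SAP 6.1 cuts its periods at drug intake. On a looser reading, an event that spans the dose would fall under both SAP rules, which also needs settling.

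**What a row 3 event loses.** SAP 7.8.1 counts subjects, not events. The event disappears from its cell in the table by system organ class and preferred term, unless the same patient has another post-dose AE with that term. The patient leaves the overall AE summary only if there is no other post-dose AE. The event stays in the listings in every case.

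**Size.** Inputs: 5 randomised patients (SAP Section 4), taken as all dosed because the safety analysis uses the treated set. One patient reclassified: 1/5 = 20 percentage points in the overall share with a treatment-emergent AE. With another post-dose AE in the same patient, the change in that share is 0. Hence at most 20 points per affected patient. The tables are by treatment group, but the split of the five over the four arms is not given, so no figure by arm follows.

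**The case against.** The strongest reply is that little is lost. Worsening of COVID-19 or of any condition present before consent is an AE in its own right and will normally be tabulated. Visits 1 and 2 may fall on the same day, so the interval between consent and dose can be very short. SAP 7.8.1 lists infusion and inhalation reactions separately from dedicated eCRF pages. With five patients and a descriptive report, the listings show every event. All of this stands, and it confines the point to row 3.

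It can also be said that the SAP assumes familiarity with the protocol and invokes its treatment-emergent concept, so the clause is inherited. This is weaker: the SAP goes on to define the concept, and its rule for pre-dose events applies to all of them without exception. SAP 5.4.1 and 5.4.2, however, are not visible in the public text, so a worsening rule there cannot be excluded. If there is one, 7.8.1 would still need to be reconciled with it.

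A reader might infer more: that post-dose worsening in general drops out of the safety tables, and with it any sign of antibody-dependent enhancement or airway irritation. The documents do not support that, for the reasons in the first paragraph. A reader might also put a size on each arm, such as 2 points per patient with 50 per arm, or 50 to 100 points in arms of one or two patients. The first uses a population to which this SAP never applies, since it was written for the terminated Phase II. The second assumes an allocation that is not reported.

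**Conclusion.** The conflict between protocol 7.2.6 and SAP 7.8.1 is real, and the visible SAP text does not declare it. Its reach is small: AEs with onset between consent and dosing that deteriorate after dosing and are held as one record. Such an event would be missing from the summary tables as described above, but not from the listings. The size is at most 20 percentage points in the overall share for one affected patient, and the number of affected patients may be zero.

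This rests on three assumptions: that occurring before intake means onset before intake, that all five randomised patients were dosed (a smaller treated set would make the step larger), and that the unseen SAP sections hold no worsening rule.

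The database was unblinded on 7 July 2021 (SAP Section 8) and the SAP is dated 19 October 2021. A reader might infer that the definition was narrowed with knowledge of the data. The documents give only the order of dates and no sign of intent. The order is a reason to state the rule openly, nothing more.

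**What to change.** In SAP 7.8.1, add the protocol 7.2.6 clause: an AE that starts before drug intake and deteriorates between drug intake and the end of the residual effect period is treatment-emergent and enters the overall summary and the tables by system organ class and preferred term. State how deterioration is identified, either from recorded intensity or from a separate post-dose record of the worsening. Restrict the listings-only rule to pre-dose AEs that do not worsen. If leaving the clause out was intended, declare it in SAP Section 4 with the reason.

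The cost is about one sentence of text and a flag derived from the AE records that exist. AE counts may rise slightly. If the CRF holds only one intensity per AE and worsening is always a new record, the flag adds no events and the sentence only aligns the two documents.

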7.8.2 Laboratory data

Laboratory data will be listed. No summary tables are planned.

The analyses of laboratory data will be based on BI standards. It will be based on SI units. All analyses will be performed on the treated set. E-dish plots will be provided for ALT and AST.

7.8.3 Vital signs

Vital signs will be listed. No summary tables are planned.

7.8.4 ECG

Not applicable.

7.8.5 Others

To support the clinical trials disclosure process special safety displays may be necessary, e.g. the number of non-serious adverse events. All required outputs (including the following information) will be included in Appendix 16.1.13.1 of the CTR:

- Number of subjects included by country
- Number of subjects inside (member states) and outside the EU (third countries)
- Frequency of serious drug-related AEs by treatment, primary system organ class and preferred term.
- Frequency of serious AEs
- Frequency of non-serious AEs with incidence >5% in any treatment arm

8. TIMEPOINT OF RELEASE OF TREATMENT INFORMATION

In phase II, it was planned to release the treatment information for interim analysis to the sponsor. Following the decision to terminate the study early, the database was unblinded on 7th July 2021, while patients were still followed in the study.

 TSAP for BI Trial No: 1487-0001
 Page 20 of 25

 Proprietary confidential information © 2021 Boehringer Ingelheim International GmbH or one or more of its affiliated companies

9. **REFERENCES**

I I	CPMP/ICH/363/96: "Statistical Principles for Clinical Trials", ICH Guideline Topic E9,
	Note For Guidance on Statistical Principles for Clinical Trials, current version.
I I	KMED-BDS-HTG-0035: "Handling of Missing and Incomplete AE Dates", current version KMED.

10. ADDITIONAL SECTIONS

10.1 EXAMPLE CODE

The provided sample code will have to be modified to suit the needs of the corresponding analysis.

10.1.1 Time-weighted average change in viral load

```
%MACRO auc (idvar =, dsname =, timevar =, yvar =, resultds =);
```

%LOCAL lastid;

%* All data mapulations are to be made outside of the macro;

%* Sort dataset -> 1st data point is the starting point;

PROC SORT DATA = &dsname OUT = _tmp;

BY &idvar &timevar;

RUN;

```
%* Get last idvar;
```

```
DATA _null_;
```

```
y = COMPBL ("&idvar");
```

```
y1 = COMPRESS(y);
```

```
n = LENGTH(y) - LENGTH(y1);
```

```
CALL SYMPUT ('lastid', COMPRESS (PUT (n+1, 5.)));
```

RUN;

```
%PUT lastid = &lastid;
%LET lastvar = %SCAN (&idvar, &lastid, %STR ( ));
```

```
DATA _tmp1;

SET _tmp;

RETAIN _ltime _lyvar _difftime _mintime;

BY &idvar;

IF FIRST.&lastvar THEN DO;

_ltime = &timevar;

_lyvar = &yvar;

_difftime = .;

_mintime = &timevar;

END;

IF NOT FIRST.&lastvar THEN DO;

auccomp = 0.5 * (&yvar + lyvar) * (&timevar - ltime);
```

```
diff = (&yvar - _lyvar);
difft = (&timevar - _ltime);
_ltime = &timevar;
_lyvar = &yvar;
IF last.&lastvar THEN _difftime = &timevar - _mintime;
OUTPUT;
END;
N:
```

RUN;

```
PROC SUMMARY DATA = tmp1;
```

BY &idvar;

VAR auccomp;

```
OUTPUT OUT = &resultds._pre SUM = auc;
```

RUN;

DATA &resultds;

```
MERGE &resultds._pre _tmp1 (WHERE = (_difftime NE .) KEEP = &idvar
_difftime);
```

```
BY &idvar;
auc = auc / _difftime;
RUN;
%MEND;
```

%auc (idvar = subject swab_type gene, dsname = rawdata3, timevar = day, yvar = log_cp_ml_d, resultds = auc_result);

10.2 DEFINITION OF HIGH RISK OF PROGRESSION TO SEVERE COVID-19 AS PER NIH TREATMENT GUIDELINE

According to the NIH COVID-19 Treatment Guidelines, version dated April 8, 2021, high risk of progression to severe COVID-19 is defined as patients who meet at least one of the following criteria:

- Have a BMI \geq 35
- Have chronic kidney disease
- o Have diabetes
- Have immunosuppressive disease
- Are currently receiving immunosuppressive treatment
- \circ Are ≥ 65 years of age
- Are \geq 55 years and <65 years of age AND have
 - cardiovascular disease, OR
 - hypertension, OR
 - chronic obstructive pulmonary disease/other chronic respiratory disease.

001-MCS-50-415_RD-01 (3.0) / Saved on 18 Jan 2021

 TSAP for BI Trial No: 1487-0001
 Page 24 of 25

 Proprietary confidential information © 2021 Boehringer Ingelheim International GmbH or one or more of its affiliated companies

Risk factor	Dictionary (level)	Code (label)
Chronic kidney disease	MedDRA (PT)	10064848 (Chronic kidney disease)
Diabetes type 1 and type 2	MedDRA (PT)	10067584 (Type 1 diabetes mellitus) 10067585 (Type 2 diabetes mellitus)
Immunosuppressive disease	MedDRA (PT)	10061598 (Immunodeficiency) 10080575 (Solid organ transplant)
Cardiovascular disease	MedDRA (PT)	10007649 (Cardiovascular disorder)
Hypertension	MedDRA (PT)	10020772 (Hypertension)
Chronic obstructive pulmonary disease	MedDRA (PT)	10009033 (Chronic obstructive pulmonary disease)
Other chronic respiratory disease	MedDRA (PT)	10038683 (Respiratory disorder) 10011762 (Cystic fibrosis) 10037383 (Pulmonary fibrosis) 10003553 (Asthma) From baseline conditions page: 10022611 (Interstitial lung disease) 10037400 (Pulmonary hypertension)
Immunosuppressive treatment	WHODrug (SDG)	0000000186 (Immunosuppressant drugs) For prednisone, doses below 20mg will not be considered as risk factor.

Table 10.2: 1 Dictionary codes for risk factors based on comorbidities or concomitant medications - Risk factor definition as per NIH treatment guidelines

 TSAP for BI Trial No: 1487-0001
 Page 25 of 25

 Proprietary confidential information © 2021 Boehringer Ingelheim International GmbH or one or more of its affiliated companies

HISTORY TABLE 11.

History table Table 11: 1

Version	Date (DD-MMM- YY)	Author	Sections changed	Brief description of change
1	19-10-2021		None	This is the final TSAP
